A.5 DO-MoST may improve outcomes. Having noted the lack of evidence-based strategies to improve AUD treatment utilization (initiation, engagement) and outcomes (less or no drinking; better health) among medical-surgical inpatients with AUDs, we hypothesize that VHA may benefit from a patient-centered approach in the real-world clinical situation of medical-surgical inpatients having inadequate treatment of their AUDs. This approach is “Drinking Options - Motivate, Shared Decisions, Telemonitor” (DO-MoST). We hypothesize (Figure 1) that DO-MoST, begun during the inpatient episode, will facilitate the transition to AUD help that is evidence-based (i.e., behavioral and/or pharmacological treatment, mutual-help groups) and improve outcomes. DO-MoST has 3 components: 1. MI to motivate patients to change drinking and initiate help; 2. Use of a Decision Aid for patients to choose the type of evidence-based help they prefer and need; and 3. Telemonitoring (TM) to support and monitor patients’ initiation of and engagement in their preferred modality of help; or, for patients not motivated to change drinking and initiate help, TM to continue to engage in MI. MI is a patient-centered counseling approach for behavior change, used typically when patients feel ambivalent, allowing counselors to have goals for counseling while acknowledging and exploring variations in individuals’ commitment to, and interest in, changing behavior. MI has evidence of efficacy in treating addictions in other settings.

[figure not shown]

Figure 1. Conceptual model of Drinking Options - Motivate, Shared Decisions, Telemonitor (DO-MoST).

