Randomized trials have compared intervening with medical patients with unhealthy alcohol use using a one-time in-person session to address drinking, to the session plus subsequent "booster" sessions. Patients in booster conditions had significantly better alcohol outcomes than patients without boosters, e.g., reductions in alcohol-related negative consequences such as injuries. However, these studies were conducted mainly with hazardous or harmful drinkers. Another study of medical inpatients identified as unhealthy alcohol users (including alcohol dependence) in Taiwan comparing UC to intervention (in-person session during hospitalization, plus up to 2 booster sessions), found that intervention patients had better 1-year alcohol outcomes (reduced consumption, drinking days, heavy drinking episodes), and that, within the intervention group, the more sessions attended, the more likely patients were to seek treatment and improve on alcohol outcomes. Benefits of alcohol interventions during hospitalization are more likely to persist if interventions extend post-discharge. A systematic review of interventions for heavy drinking inpatients found that multi-session, but not single-session, BIs were associated with reduced drinking up to one year later. In addition, telephone-monitored addiction patients were more likely to report abstinence on days they made calls than on those they did not, and less likely to increase on drinking days per week than controls. Post-discharge monitoring sessions for 3 months are well-attended by patients and associated with better substance use outcomes partly via patients' greater self-efficacy for avoiding substance use in the monitoring condition that offers cumulative support and encouragement. The number of monitoring sessions for the present study is designed to enhance the intervention's effect while keeping the intervention brief enough to be practical.

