Telephone sessions (in Appendix) will be adapted from our current manualized protocol using MI with detox inpatients after an in-person session; the in-person session helps overcome the potential barrier of being less likely to engage in phone calls with a provider patients have never met. Patients in DO-MoST will be expected to complete one 15-minute phone call every 2 weeks for 12 weeks by answering calls at predetermined times. When patients fail to answer a call, the Decision Coach will make at least 2 more attempts to contact the patient for that scheduled contact, and when successful, the initial failure will be discussed. During each telephone session, patients will complete the Progress Assessment Worksheet which includes drinking and help preferences, and questions about recent substance use, treatment and mutual-help. TM when “no” to help. Patients indicating during the inpatient session that they do not want to change drinking or initiate help will receive MI during the biweekly telephone calls. We expect that patients who choose not to initiate help will participate in TM because experience in our own projects agrees with the research literature that even medical patients who report they are doing well are more satisfied with their care when providers continue to monitor and support them. Decision Coaches will be trained to use phone calls as part of DO-MoST to positively reinforce even small steps toward recovery and to react non-judgmentally to set-backs. Guidelines for phone sessions state that the patient’s status should be considered in how to proceed. The Decision Coach will explain the overall approach (not trying to change the patient), elicit self-motivational statements, and use reflection. Elicited will be the perceived possible benefits of help and likely negative consequences of not obtaining help for alcohol use. Decision Coaches will seek to obtain whatever commitment to obtaining help that is possible. They will focus on patients’ views of negative aspects of using alcohol by eliciting patients’ personal goals, helping the patient assess how drinking hinders progress toward those goals, and giving personalized feedback on the hazards and risks of drinking. To foster commitment to change drinking behaviors, Decision Coaches will use the techniques of developing the discrepancy between current behaviors and values. As sessions progress, Decision Coaches will help patients reassess their drinking-related behaviors and the effectiveness of aspects of their plans. Later telephone sessions (guided by patients’ progress) will focus on continuing to build patients’ successes at achieving values, supported and assisted by the Decision Coach. Importantly, in our prior work using TM following an inpatient psychiatry stay for those with dual diagnoses, we were successful in retaining individuals who were abstinent and those who relapsed. Some patients who initially do not prefer to initiate help may subsequently choose help initiation (Figure 1), in which case the protocol immediately below will be used.

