B.3.7 During-treatment assessments. The start-up period in which Decision Coaches are trained will be important to establishing the fidelity with which DO-MoST is delivered. To assess the integrity of the DO-MoST condition throughout the study, sessions will be evaluated against a protocol checklist (adapted from Drs. [name] and [name]'s Decision Aid studies, and from the PIs' previous and ongoing MI-TM studies with psychiatry and detox inpatients). All phone sessions will be audiotaped (with appropriate consent). Phone sessions will be evaluated by [name] (assisted by the PIs) under the following schedule: (1) the first 15 phone calls for each Decision Coach will be assessed for protocol fidelity, and the Coach will be provided corrective feedback, and (2) eight calls will be reviewed at random each month to ensure ongoing fidelity of the intervention. No problems with adherence or responding appropriately to feedback were noted previously.

B.3.8 Follow-up assessments. Patients' follow-up data will come from administrative data in the VA Corporate Data Warehouse (CDW), and patient self-report. CDW data will cover behavioral health provided within primary care and addiction specialty care encounters, i.e., entry into addiction treatment, and types, timings, and durations of treatments. Self-report data will include drinking and help preferences; use of alcohol (and other drugs); medical status; help participation; other functioning; and potential explanatory mechanisms linking help to outcomes, i.e., motivation, commitment, and self-efficacy to change alcohol-related behaviors; decisional conflict about help.

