**B.3.12 Examine mechanisms (reasons DO-MoST is effective).** Alcohol help initiation and engagement will be examined as mediators between condition and outcomes. We will conduct a series of regression models (controlling for covariates, e.g., baseline value of the dependent variable) that correspond to a hypothesized causal sequence among (1) DO-MoST, (2) alcohol help utilization, and (3) better alcohol and medical outcomes. First, the dummy variable representing DO-MoST is the independent variable and the dependent variable is the outcome (e.g., abstinence, percent of heavy drinking days). In the second regression, DO-MoST is the independent variable and the dependent variable is the potential mediator (e.g., duration of alcohol outpatient help). In the third regression the potential mediator is the independent variable and the dependent variable is the outcome. If the coefficient for DO-MoST or potential mediator is significant in all cases, we will proceed. In the final regression, DO-MoST is entered simultaneously with the utilization variable as predictors of the outcome. If the coefficient for utilization is significant and the coefficient for DO-MoST on the outcome is reduced, then we will conclude that a mediating effect of utilization is supported, and evaluate whether the indirect effect of DO-MoST on the outcome via treatment is significant.

We will also determine if increases in treatment utilization associated with DO-MoST are mediated by the mechanisms of reduced decisional conflict and increased motivation, commitment, and self-efficacy. We will conduct a series of regression models that correspond to a hypothesized causal sequence among (1) DO-MoST (vs. UC), (2) the potential mechanisms, and (3) use of alcohol treatment, and control for covariates. Analyses will use the same general linear model approach described in the previous paragraph. We will conduct regression analyses (covariates controlled) to examine associations of DO-MoST dose (number of phone sessions completed) with patients' outcomes at follow-ups, using methods (e.g., instrumental variables) to account for possible problems associated with endogeneity. We will explore whether less intensive (e.g., 3-session) doses of DO-MoST are as effective as the full, 6-session dose.

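### The rule for concluding that help use mediates the effect on drinking takes no account of motivation, commitment or self-efficacy, so it can declare mediation when help has no effect

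*Combined protocol and SAP*

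**What the plan says.** All references are to the combined protocol and SAP.

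- **What the intervention targets.** A.5 gives the purpose of its motivational interviewing (MI) as "MI to motivate patients to change drinking and initiate help": one lever, two targets. A.5 also credits an earlier telephone-monitoring programme's benefit partly to "greater self-efficacy for avoiding substance use in the monitoring condition that offers cumulative support and encouragement". In B.3.4, for patients who have said no to help, the instruction is: "To foster commitment to change drinking behaviors, Decision Coaches will use the techniques of developing the discrepancy between current behaviors and values".
- **How mediation by help is tested (B.3.12).** "Alcohol help initiation and engagement will be examined as mediators between condition and outcomes". There are four regressions, run "controlling for covariates, e.g., baseline value of the dependent variable". The last is specified as: "In the final regression, DO-MoST is entered simultaneously with the utilization variable as predictors of the outcome". If help is significant and the DO-MoST coefficient falls, "then we will conclude that a mediating effect of utilization is supported", and the indirect effect is then tested.
- **Where motivation, commitment and self-efficacy appear.** B.3.12 gives them a separate chain that runs from DO-MoST through these variables to treatment use and stops there. B.3.8 gives them another role: "potential explanatory mechanisms linking help to outcomes, i.e., motivation, commitment, and self-efficacy to change alcohol-related behaviors".
- **Confounding.** Endogeneity methods are mentioned only for the analysis of number of phone sessions. No sensitivity analysis is planned for confounding between help use and outcome.

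**The concern.** Randomization makes the arms comparable. It does not make users and non-users of help comparable within an arm. By the plan's own account, motivation, commitment and self-efficacy drive both help-seeking and drinking, so more motivated patients will tend both to seek help and to drink less. The final regression then shows a help coefficient even if help has no effect.

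The requirement that the DO-MoST coefficient be reduced gives no protection. In linear regressions on the same patients and covariates, the total effect minus the direct effect equals (arm effect on help) × (help coefficient). Once DO-MoST raises help use and the help coefficient has the expected sign, the reduction follows automatically.

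At stake is the answer to a question the analysis overview (B.3.11) sets itself: why DO-MoST works. A benefit of counselling, or plain differences between patients, could be reported as a benefit of treatment use.

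**Working it through.** **Inputs from the plan.** Effect size 0.50 for help and alcohol outcomes, and N = 156 at 1:1 (B.3.1). Follow-up target of at least 70% (B.3.9): 156 × 0.70 = 109, taken as 110.

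**Assumed, because not stated.** Two-sided 5% level. Motivation has within-arm correlation r with help and −r with drinking. The true effect of help on drinking is zero.

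**Plan's own figure.** There is none for the mediation analysis. N = 156 serves only as the size for the check.

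**Step 1, bias.** With motivation omitted, the standardized within-arm help coefficient is about −r × r = −r². At r = 0.3, 0.4 and 0.5 that is −0.09, −0.16 and −0.25. Simulation with baseline drinking as covariate gave −0.09, −0.15 and −0.24.

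**Step 2, chance that help is significant in the final regression.** The standard error is about 1/√N, so z = r²√N and P(final) = Φ(z − 1.96). At r = 0.4 and N = 156: z = 0.16 × 12.49 = 2.00, P = 0.515.

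**Step 3, chance that both arm effects are significant.** Each has z = 0.5 × √(N/4). For N = 156 this is 3.12, power 0.877, squared 0.77. For N = 110 it is 2.62, power 0.746, squared 0.557. The help-only regression rarely fails once these hold.

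**Step 4, whole rule.** P ≈ Step 2 × Step 3. At r = 0.4: 0.515 × 0.77 = 0.40 for N = 156; 0.389 × 0.557 = 0.22 for N = 110.

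| r | N=156 formula | N=156 simulated | N=156 simulated, Sobel also significant | N=110 formula | N=110 simulated |
|---|---|---|---|---|---|
| 0 | 2% | 2% | 1% | 1% | 1% |
| 0.2 | 6% | 6% | 2% | 3% | 3% |
| 0.3 | 16% | 15% | 7% | 9% | 8% |
| 0.4 | 40% | 39% | 22% | 22% | 20% |
| 0.5 | 68% | 65% | 48% | 41% | 41% |

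Simulations used 3,000 trials per case (error about ±2 points). The Sobel test stands in for the plan's indirect-effect test, which the text does not name.

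**Step 5, other settings.**
- A simulation set up with path coefficients instead of correlations, N = 156: about 3%, 16%, 44% and 77% at 0.2, 0.3, 0.4 and 0.5.
- Smaller arm effects (0.25 SD direct on drinking, 0.5–0.8 SD on motivation, N = 110–156): 1–5%, 5–22% and 14–54% at 0.3, 0.4 and 0.5.
- Help as yes/no, N = 156: 9%, 23% and 48% at 0.3, 0.4 and 0.5.
- DO-MoST does not change motivation at all, r = 0.5, N = 156: 64%. Ordinary differences between patients are enough.

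**Step 6, what adjustment does (r = 0.5, N = 156).** Unadjusted, 65%. With baseline motivation only, 54%. With post-randomization motivation that precedes help and has no measurement error, 2%. With reliability 0.9, 0.8 and 0.7: 5%, 10% and 15%.

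**Step 7, the opposite ordering.** Suppose help truly works, but wholly through motivation, with paths 0.4 and 0.5 (assumed). Unadjusted, the help coefficient is 0.4 × 0.5 = 0.20, z = 0.20 × 12.49 = 2.50, and help is detected with probability Φ(0.54) = 0.70. With same-period motivation added, the coefficient is zero and detection falls to the 5% error rate. A simulation of this situation gave 67% falling to 5%.

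**The case against.** **The covariate list is open.** True: adjustment is allowed. But none of these scores is named, and the only example given is a baseline value. Step 6 shows that baseline motivation removes only part of the bias.

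**Adjusting for follow-up motivation could do more harm.** This is the strongest objection, and it stands. B.3.8 places these variables after help; if that is right, Step 7 applies and adjustment hides a real effect. They are measured at baseline and at 3, 6 and 12 months, so no score falls between baseline and month 3, when coaching takes place and early help begins. A reader might infer that the motivation-adjusted regression should become the decision rule and would restore the nominal error rate. The documents do not support that: the order of the variables is unsettled, and brief scales carry measurement error.

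**The consequence is limited.** Also true. The plan would conclude that there is a mediating effect, not that help is the whole explanation. DO-MoST stays in the final model, so a remaining direct effect would be visible. Implementation is informed separately by the Aim 3 interviews. A reader might infer that roll-out would be misdirected, or that the main results are biased; neither follows. Hypotheses 1–3 rest on the randomized comparison.

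**The rates rest on assumed correlations, and a further test follows.** Correct on both counts. The indirect-effect test lowers the rates, but at r = 0.4 and N = 156 it still leaves 22%. Figure 1, the conceptual model, is not available in the text reviewed, so the intended ordering may be clearer there.

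**Conclusion.** The concern holds for the mechanism analysis in B.3.12. The plan says coaching acts on drinking and on help-seeking, then infers mediation by help from a model that names none of the variables joining the two, with no check for confounding.

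The chance of falsely declaring mediation is close to nominal at correlations of 0.2 or below (1–6%), roughly 20–45% at 0.4, and higher at 0.5 (41–77% across the two set-ups with larger rates). It is lower if the indirect effect must also be significant, and lower with smaller arm effects. These figures assume a 5% level, one common cause and a true help effect of zero. The documents give no correlations, so the actual rate is unknown.

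The randomized comparisons of DO-MoST with usual care are untouched.

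**What to change.** Amend B.3.12 as follows.

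1. Name the baseline Readiness Ruler, Commitment to Abstinence and Brief Situational Confidence scores as covariates in the help-to-outcome regressions, and state that this removes only part of the bias.
2. Add a lagged model: help between months 3 and 6 predicts drinking after month 6, adjusting for arm, for help and drinking in months 0–3, and for month-3 motivation, commitment and self-efficacy. The Timeline Follow-Back covers the time since the previous interview, so these windows are already collected. Because the month-3 scores may themselves be changed by DO-MoST, define the indirect effect accordingly (an interventional indirect effect).
3. For help in months 0–3, report the result with and without the month-3 scores as a sensitivity range, not as a single decision rule.
4. State that mediation is supported only if both the help coefficient and the indirect effect hold in the lagged model. Otherwise report an association that motivation may explain.
5. Reconcile B.3.8 with B.3.12 on whether these variables come before or after help.

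**Cost.** Plan wording and a few regressions on data already being collected. Some precision is lost, measurement error in brief scales leaves residual bias, and the lagged model does not cover early initiation, so the claim about early help becomes less definite.

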## **B. Research Design and Methods**

**B.1 Overview.** A goal of this study is to make available a validated decision aid to enable providers to assist medical-surgical inpatients with AUD to make decisions about AUD help (Aim 1). Another goal is to determine whether adding DO-MoST (which incorporates MI, use of this decision aid, and TM) to usual inpatient medical-surgical care for Veteran inpatients with AUD, increases participation in AUD help (Aim 2, Hypothesis 1), improves alcohol use and medical outcomes (Aim 2, Hypothesis 2), and reduces subsequent acute care utilization (Aim 2, Hypothesis 3). Patients will be followed at 3 months (end of intervention for those in DO-MoST), and 6 and 12 months post-discharge. The project will also conduct a qualitative process evaluation to inform the future implementation of DO-MoST beyond the two sites in this project (Aim 3).

**B.2 Aim 1: Adapt an AUD Decision Aid.** We will adapt a Decision Aid currently being used with AUD patients in primary care settings so that it is applicable for Veterans with AUDs in medical-surgical inpatient settings. The existing Decision Aid meets International Patient Decision Aid Standards, i.e., provides information about options and probable effects of taking each option (including course of disorder if no action is taken); presents the latest scientific evidence and options in a balanced way; uses plain language; supports the patient to clarify

and express values related to the decision; uses patients' personal histories to communicate options and model values clarification; provides guidance in patients' deliberations and communication of concerns or decisions; enables disclosure of conflicts of interest. Decision aids are tools to help health care consumers understand and clarify their choices and preferences in regard to a discrete decision. They list possible interventions, outcomes that might occur, and the likelihood of these outcomes. Decision aids are offered in a variety of forms; this one is on paper. Decision aids improve patients' knowledge of treatment options, realistic expectations of treatment outcomes, comfort with choices, and agreement between values and choices, and decrease patients' decisional uncertainty.

Using recommended methods (e.g., updated systematic review of the most recent literature on the efficacy and risks of evidence-based addiction treatments) and sample sizes, with the prototype, at each site we will conduct alpha testing (face-to-face semi-structured interviews) with 5 medical-surgical inpatients with AUDs, and 4 providers (physicians, nurses, and social workers), in the same units in which the RCT will be conducted. We will also observe (5 per site) inpatient nurses and social workers as they administer alcohol screening and brief intervention (ORYX procedures required by the Joint Commission). Provider recruitment will follow procedures used successfully in our other projects interviewing treatment providers (e.g., QUERI RRP 12-525, which recruited 100% [N=30] of the target sample size). (Recruitment of non-providers is in Section B.3.4.) At each site, the PIs will contact by email each inpatient unit staff member to be interviewed to briefly explain the purpose of the project and invite the individual to participate. Emails will be followed with a phone call to answer any questions the staff member may have and schedule an interview time. If emails fail at contact, we will make phone calls or visit the inpatient unit in person. Staff members will provide informed consent prior to interview. Providers (prohibited by VA rules from receiving remuneration) will be interviewed in person while on or off duty, as they prefer.

Alpha testing will determine the ease and difficulty of understanding the Decision Aid (whether it needs to be even less complex) and the extent to which it is complete and applicable to the specific target population. Using cognitive "think-alouds," interviewees will be asked for their thoughts about the Decision Aid while reviewing the contents, e.g., parts that are hard to understand, extent to which patients would be sufficiently informed and supported, places needing more information. Think-alouds will include reactions about reading levels, use of technical terms and acronyms, and layout. Based on feedback during alpha testing, the study team will adapt the Decision Aid. The Decision Aid will then be piloted with 5 patients (not in the alpha test) and 4 providers (in and not in the alpha test) at each site for finalizing it before use in the RCT.

